8 SAFETY ASSESSMENTS

8.1 Adverse Events

An AE is defined as any untoward medical occurrence in a clinical investigation participant administered a pharmaceutical product, which does not necessarily have a causal relationship with this treatment. An AE can therefore be any unfavorable and/or unintended sign (including an abnormal laboratory finding), symptom, or disease temporally associated with the use of an investigational medicinal product, whether or not related to the investigational medicinal product. All AEs, including observed or volunteered problems, complaints, or symptoms, are to be recorded on the appropriate eCRF.

AEs, which include clinical laboratory assessment variables, will be monitored and documented from the time of first dose of study treatment until completion of Visit 7. Participants should be instructed to report any AE that they experience to the Investigator, whether or not they think the event is due to study drug. Beginning at the date of the first dose of study treatment, Investigators should make an assessment for AEs at each visit and record the event on the appropriate AE eCRF.

Wherever possible, a specific disease or syndrome rather than individual associated signs and symptoms should be identified by the Investigator and recorded on the eCRF. However, if an observed or reported sign or symptom is not considered a component of a specific disease or syndrome by the Investigator, it should be recorded as a separate AE on the eCRF. Additionally, the condition that led to a medical or surgical procedure (eg, surgery, endoscopy, tooth extraction, or transfusion) should be recorded as an AE, not the procedure itself.

Any medical condition already present at the date of the first dose of study treatment should be recorded as medical history and not be reported as an AE unless the medical condition or signs or symptoms present at baseline changes in severity, frequency, or seriousness at any time during the study. In this case, it should be reported as an AE.

Clinically significant abnormal laboratory or other examination findings (eg, ECG) that are detected during the study or are present at the date of the first dose of study treatment and significantly worsen during the study should be reported as AEs, as described below. The Investigator will exercise his or her medical and scientific judgment in deciding whether an abnormal laboratory finding or other abnormal assessment is clinically significant. Clinically significant abnormal laboratory values occurring during the study will be followed until repeat tests return to normal, stabilize, or are no longer clinically significant. Abnormal test results that are determined to be an error should not be reported as an AE. Laboratory abnormalities or other abnormal clinical findings (eg, ECG abnormalities) should be reported as an AE if any of the following are applicable:

- If an intervention is required as a result of the abnormality;
- If action taken with the study drug is required as a result of the abnormality; or
- Based on the clinical judgment of the Investigator.

8.1.1 Adverse (Drug) Reaction

All noxious and unintended responses to a medicinal product related to any dose should be considered an adverse drug reaction. "Responses" to a medicinal product means that a causal

relationship between a medicinal product and an AE is at least a reasonable possibility, ie, the relationship cannot be ruled out.

8.1.2 Unexpected Adverse Drug Reaction

An Unexpected Adverse Drug Reaction is defined as an adverse reaction, the nature or severity of which is not consistent with the applicable product information.

8.1.3 Assessment of Adverse Events by the Investigator

The Investigator will assess the severity (intensity) of each AE as mild, moderate, or severe, and will also categorize each AE as to its potential relationship to study drug using the categories of yes or no.

Assessment of severity

Mild – An event that is easily tolerated and generally not interfering with normal daily activities.

Moderate – An event that is sufficiently discomforting to interfere with normal daily activities.

Severe – An event that is incapacitating with inability to work or perform normal daily activities.

Causality assessment

The relationship of an AE to the administration of the study drug is to be assessed according to the following definitions:

No (unrelated, not related, unlikely to be related) – The time course between the administration of study drug and the occurrence or worsening of the AE rules out a causal relationship and another cause (concomitant drugs, therapies, complications, etc) is suspected.

Yes (possibly, probably, or definitely related) – The time course between the administration of study drug and the occurrence or worsening of the AE is consistent with a causal relationship and no other cause (concomitant drugs, therapies, complications, etc) can be identified.

The definition implies a reasonable possibility of a causal relationship between the event and the study drug. This means that there are facts (evidence) or arguments to suggest a causal relationship.

The following factors should also be considered:

• The temporal sequence from study drug administration-

The event should occur after the study drug is given. The length of time from study drug exposure to event should be evaluated in the clinical context of the event.

• Underlying, concomitant, intercurrent diseases-

Each report should be evaluated in the context of the natural history and course of the disease being treated and any other disease the participant may have.

Concomitant drug-

The other drugs the participant is taking or the treatment the participant receives should be examined to determine whether any of them might be recognized to cause the event in question.

• Known response pattern for this class of study drug-

Clinical and/or preclinical data may indicate whether a particular response is likely to be a class effect.

• Exposure to physical and/or mental stresses-

The exposure to stress might induce adverse changes in the recipient and provide a logical and better explanation for the event.

The pharmacology and PK of the study drug-

The known pharmacologic properties (absorption, distribution, metabolism, and excretion) of the study drug should be considered.

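### Protocol 8.1.3 defines the yes/no causality rating so that an event with plausible timing and another identifiable cause fits neither category, and this conflicts with 8.1.1

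*Protocol*

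**What the plan says.** Protocol 8.1.3 asks the investigator to categorize each adverse event's relationship to study drug "using the categories of yes or no". The relationship "is to be assessed according to the following definitions", and two definitions follow, each joining two conditions with *and*:

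- **Yes**: the time course "is consistent with a causal relationship and no other cause (concomitant drugs, therapies, complications, etc) can be identified".
- **No**: the time course "rules out a causal relationship and another cause (concomitant drugs, therapies, complications, etc) is suspected".

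Each category also carries labels. One opens "Yes (possibly, probably, or definitely related"; the other opens "No (unrelated, not related, unlikely to be related".

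The section then says that the definition implies a reasonable possibility of a causal link and explains the phrase: "This means that there are facts (evidence) or arguments to suggest a causal relationship". A list introduced by "The following factors should also be considered" covers timing, other diseases, other drugs, class effects, stress and pharmacology.

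Protocol 8.1.1 uses the same phrase to define an adverse drug reaction, but equates it with being unable to exclude the relationship. Protocol 8.1.2 and 8.5 build on the term adverse reaction.

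The rating is used downstream. SAP 3.6.1 tabulates study drug related TEAEs and TESAEs and gives no definition of related of its own. Protocol 8.3 requires all SAEs to be reported up to 30 days after the last dose. After that, it requires a report only for SAEs that the investigator considers related.

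**The concern.** A binary rating needs two categories that between them cover every event. Here each definition sets two conditions, and an event can satisfy one condition from each side. The obvious case is an event whose timing fits the drug but for which another cause can also be named. It is not a far-fetched case: every participant takes a high-intensity statin (Protocol 4.1), and the definitions themselves list concomitant drugs, therapies and complications as other causes.

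At stake is the consistency of the drug-related event counts across roughly 20 sites, and possibly which late SAEs generate a formal report. There is also a direct conflict within the protocol: an event can be an adverse drug reaction by 8.1.1 while failing the definition of a related event in 8.1.3.

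**Working it through.** The plan gives no figure to reproduce. The check is to enumerate the cases and then compare the two sections.

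**Step 1. Enumerate.** Cross the two conditions used in 8.1.3: time course (compatible with the drug, or excludes it) and other cause (present or absent). The definitions are:

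- Yes = compatible AND no other cause
- No = excluded AND other cause

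| Time course | Other cause | Meets Yes | Meets No | Result by definition |
|---|---|---|---|---|
| Compatible | Absent | yes | no | Yes |
| Excluded | Present | no | yes | No |
| Compatible | Present | no | no | neither |
| Excluded | Absent | no | no | neither |

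Two of the four cells have no category, and no cell has both. These are logical cells, not proportions of events.

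**Step 2. Apply the labels.** When timing excludes the drug and no other cause is known, the label *unrelated* gives No. When timing is compatible and another cause is present, *possibly* (under Yes) and *unlikely* (under No) can both describe the event. One of the four cells therefore stays open.

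**Step 3. Apply the rest of 8.1.3.** The factors direct the investigator to weigh other drugs and diseases, but none says which category follows. They are introduced as additional considerations, so they supplement the definitions rather than replace them.

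**Step 4. Compare with 8.1.1.** The two sections explain reasonable possibility differently. In 8.1.1 it is enough that a link cannot be excluded. In 8.1.3 there must be evidence or arguments pointing towards a link. Take the open cell and suppose that the link cannot be excluded:

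- By 8.1.1 the event is an adverse drug reaction.
- By the literal Yes in 8.1.3 it is not related, because another cause can be identified.
- By the literal No in 8.1.3 it is not unrelated either, because the timing does not exclude the drug.

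**Step 5. Trace the uses.** The rating feeds the drug-related TEAE and TESAE summaries in SAP 3.6.1. It may also influence reporting under Protocol 8.3 once the 30 days have passed. It does not enter adverse event recording, which runs to Visit 7 regardless of cause (8.1), nor the all-causality summaries, SAE reports within 30 days, or any efficacy analysis.

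**The case against.** The best reply is that causality rating is a clinical judgement and 8.1.3 supplies what it needs. An investigator who thinks an event possibly related finds that word under Yes, and the factors require competing causes to be weighed. Protocol 8.3 does not cite the 8.1.3 definitions, so an investigator who considers a late SAE related must report it on those words alone. A late SAE without a formal report would still be recorded as an adverse event up to Visit 7 and seen in monitoring (11.4). The eCRF completion procedures that 11.4 says are reviewed with sites are not among the documents and may already settle the matter. The statin argument is also limited, because the required stable dose (4.1, 5.6.2) makes the statin a less ready explanation for a new event.

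Much of this stands and limits the consequence. It does not close the gap: room for judgement is not a rule for the mixed case, and separate completion procedures would leave 8.1.1 and 8.1.3 in conflict.

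Three stronger readings are tempting but unsupported:

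- *Related events will be under-counted.* The open case fails No as well as Yes, and *possibly* sits under Yes, so misrating could go either way.
- *The exposure can be measured as the days or visits between the end of the 30-day window and Visit 7.* Protocol 8.3 gives no end date for the duty to report related late SAEs; Visit 7 ends adverse event collection, not that duty. Such a count would also describe the 30-day rule, not the effect of the wording.
- *The arms will be rated differently.* The same rule applies in every arm of a double-blind study, and the documents give no reason to expect a difference.

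**Conclusion.** The point holds, and it is minor. The two definitions in 8.1.3 are not exhaustive, and they conflict with 8.1.1 for an event with compatible timing and a competing cause whose link to the drug cannot be excluded. The practical result is that sites may rate like events differently, in either direction. The drug-related summaries are affected directly; the effect on late SAE reports is plausible but inferred, since 8.3 rests on the investigator's view without naming the 8.1.3 definitions.

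The number and direction of affected events cannot be computed from the documents. Safety is summarized descriptively, without inference (SAP 3.6), so no test result depends on the rating.

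The conclusion assumes that investigators apply the definitions as written and that no site material outside the documents already assigns the mixed case.

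**What to change.** Reconcile 8.1.3 with 8.1.1:

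1. Remove the absence of another identifiable cause as a required condition for Yes, and keep other causes among the factors to weigh.
2. Define Yes as at least a reasonable possibility of a causal relationship, and give that phrase one meaning in both sections. Check the chosen meaning against 8.1.2 and 8.5, which rely on the same adverse-reaction term.
3. Define No as all other events, so that the two categories are exhaustive.
4. Make the *possibly* and *unlikely* labels agree with that single standard.
5. Repeat the wording in the eCRF completion guide.

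The cost is a wording amendment, which under Protocol 12.1 goes through the same review and approval as the original protocol, plus the revised guide. The change may also lead to more events being rated related and more late SAE reports.

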8.2 Serious Adverse Events

An AE or adverse reaction is considered serious if, in the view of either the Investigator or Sponsor, it results in any of the following outcomes:

- Death;
- A life-threatening AE;

Note: An AE or adverse reaction is considered "life-threatening" if, in view of either the Investigator or Sponsor, its occurrence places the participant at immediate risk of death. It does not include an event that, had it occurred in a more severe form, might have caused death.

• Requires hospitalization or prolongation of existing hospitalizations;

Note: Any hospital admission with at least 1 overnight stay will be considered an inpatient hospitalization. An emergency room or urgent care visit without hospital admission will not be recorded as a SAE under this criterion, nor will hospitalization for a procedure scheduled or planned before signing of informed consent, or elective treatment of a pre-existing condition that did not worsen from baseline. However, unexpected complications and/or prolongation of hospitalization that occur during elective surgery should be recorded as AEs and assessed for seriousness. Admission to the hospital for social or situational reasons (ie, no place to stay, live too far away to come for hospital visits, respite care) will not be considered inpatient hospitalizations.

- A persistent or significant disability/incapacity or substantial disruption of the ability to conduct normal life functions;
- A congenital anomaly/birth defect; or
- An important medical event.

Note: Important medical events that do not meet any of the above criteria may be considered an SAE when, based upon appropriate medical judgment, they may jeopardize the participant and may require medical or surgical intervention to prevent 1 of the outcomes listed above. Examples of such medical events include allergic bronchospasm requiring intensive treatment in an emergency room or at home, blood dyscrasias or convulsions that do not result in inpatient hospitalizations, or the development of drug dependency.

Serious Adverse Event Reporting - Procedures for Investigators 8.3

Initial reports
All SAEs occurring from the time of the first dose of study treatment until 30 days following the last administration of study drug must be reported to within 24 hours of the knowledge of the occurrence. After the 30-day reporting window, any SAE that the Investigator considers related to study drug must be reported to the Sponsor/designee.
To report the SAE, complete the SAE form electronically in the electronic data capture (EDC) system for the study. When the form is completed, personnel will be notified electronically by the EDC system and will retrieve the form. If the event meets serious criteria and it is not possible to access the EDC system, send an email to
or call the unumber listed below), and fax/email the completed paper SAE form to contact information listed in Section 8.6) within 24 hours of awareness. When the EDC system becomes available, the SAE information must be entered within 24 hours of the system becoming available.
Follow-up reports
The Investigator must continue to follow the participant until the SAE has subsided or until the condition becomes chronic in nature, stabilizes (in the case of persistent impairment), or the participant dies.
Within 24 hours of receipt of follow-up information, the Investigator must update the SAE form electronically in the EDC system for the study and submit any supporting documentation (eg, participant discharge summary or autopsy reports) to via fax or email. If it is not possible to access the EDC system, refer to the procedures outlined above for initial reporting of SAEs.
8.4 Pregnancy Reporting
If a participant becomes pregnant during the study or within the Safety Follow-up Period defined in the protocol, the Investigator is to stop dosing with study drug(s) immediately and the participant should be withdrawn from the study. Early termination procedures should be implemented at that time.
A pregnancy is not considered to be an AE or SAE; however, it must be reported to within 24 hours of knowledge of the event. will then provide the Investigator/site the Exposure In Utero (EIU) form for completion. The Investigator/site must complete the EIU form and fax/email it back to
If the female partner of a male participant becomes pregnant while the participant is receiving study drug or within the Safety Follow-up Period defined in the protocol, the Investigator should notify as described above.
The pregnancy should be followed until the outcome of the pregnancy, whenever possible. Once the outcome of the pregnancy is known, the EIU form should be completed and faxed/emailed to . If the outcome of the pregnancy meets the criteria for immediate classification as an SAE (ie, postpartum complication, spontaneous abortion, stillbirth, neonatal

death, or congenital anomaly), the Investigator should follow the procedures for reporting an SAE.

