2.2 Secondary Objectives

The secondary objectives of this study include the following:

- To evaluate the effect of obicetrapib, compared to placebo, at Day 56 on ApoB, non-HDL-C, and HDL-C, as an adjunct to high-intensity statin therapy;
- To assess the mean plasma levels of obicetrapib at steady state on Days 56, 84, 112, and 161; and
- To evaluate the safety and tolerability profile of obicetrapib.

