3.1.3 Safety Follow-Up Period

Participants will return to the site for a Safety Follow-up Visit (Visit 5) approximately 4 weeks after the end of the Treatment Period for safety and PK assessments.

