3.1.4 Pharmacokinetic Period

Participants will return to the site for 2 PK Visits (Visits 6 and 7) approximately 8 and 15 weeks, respectively, after the end of the Treatment Period for safety and PK assessments.

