4 SELECTION AND WITHDRAWAL OF PARTICIPANTS

4.1 Inclusion Criteria

Participants who meet all of the following criteria will be eligible to participate in the study:

- 1. Understanding of the study procedures, willingness to adhere to the study schedules, and agreement to participate in the study by giving written informed consent prior to screening procedures;
- 2. Men or women 18 to 75 years of age, inclusive, at the Screening Visit;
 - o Women may be enrolled if all 3 of the following criteria are met:
 - They are not pregnant;
 - They are not breastfeeding; and
 - They do not plan on becoming pregnant during the study;
 - O Women of childbearing potential must have a negative urine pregnancy test at the Screening Visit. Note: Women are not considered to be of childbearing potential if they meet 1 of the following criteria as documented by the Investigator:
 - They have had a hysterectomy or tubal ligation at a minimum of 1 cycle prior to signing the ICF; or
 - They are postmenopausal, defined as ≥1 year since their last menstrual period for women ≥55 years of age or ≥1 year since their last menstrual period and have a follicle-stimulating hormone (FSH) level in the postmenopausal range for women <55 years of age; and

 - O Women of childbearing potential must agree to use an effective method of avoiding pregnancy from screening to 90 days after the last visit. Men whose partners are of childbearing potential must agree to use an effective method of avoiding pregnancy from screening to 90 days after the last visit. Effective methods of avoiding pregnancy are contraceptive methods with a Pearl index of <1 used consistently and correctly (including implantable contraceptives, injectable contraceptives, oral contraceptives, transdermal contraceptives, intrauterine devices, diaphragm with spermicide, male or female condoms with spermicide, or cervical cap) or a sterile sexual partner;
- 3. Fasting LDL-C levels >70 mg/dL and TG levels <400 mg/dL at the Screening Visit; and
- 4. Currently receiving high-intensity statin therapy (atorvastatin 40 or 80 mg or rosuvastatin 20 or 40 mg) at a stable dose for 8 weeks prior to screening and intending to remain at the same stable dose throughout the study duration.

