#### 2.2 Study Design

#### 2.2.1 Overview

The population for this study includes men and women 18 to 75 years of age, inclusive, with a body mass index <40 kg/m², fasting LDL-C levels >70 mg/dL, and triglyceride levels <400 mg/dL at the Screening Visit, who are currently receiving high-intensity statin therapy.

This study will be a placebo-controlled, double-blind, randomized, Phase 2 dose-finding study to evaluate the efficacy, safety, and tolerability of obicetrapib as an adjunct to high-intensity statin therapy. This study will take place at approximately 20 sites in the United States.

The total duration for the double-blind period for each subject will be up to 25 weeks, including up to 2 weeks for Screening, 8 weeks for blinded study treatment, 4 weeks for safety follow-up, and 11 weeks for PK assessments. Please refer to Table 1 (Schedule of Procedures) below for details.

At the Screening Visit (Visit 1), participants will be required to sign an informed consent form (ICF) before any study-related procedures are performed. After signing the ICF, participants will be assessed for study eligibility.

Up to 2 weeks after the Screening Visit, participants will return to the site on Day 1 (Visit 2) and confirm study eligibility before being randomized and beginning treatment. Approximately 114 eligible participants (38 participants per treatment group) will be randomized in a 1:1:1 ratio to 1 of the following treatment groups:

• 5 mg obicetrapib (one 5 mg obicetrapib tablet + 1 placebo tablet);

- 10 mg obicetrapib (two 5 mg obicetrapib tablets); or
- Placebo (2 placebo tablets).

During the 8-week Treatment Period, the assigned study drugs will be administered by the participants orally and once daily on Day 1 to Day 56. Participants will return to the site every 4 weeks for efficacy, safety, and pharmacokinetic (PK) assessments. Participants, Investigators, the Clinical Research Organization (CRO), and the Sponsor will be blinded to all lipid results from Day 1 (Visit 2) for the first participant through database lock in order to protect blinding to treatment assignment.

Participants will return to the site for a Safety Follow-up Visit (Visit 5) approximately 4 weeks after the end of the Treatment Period for safety and PK assessments.

Participants will return to the site for 2 PK Visits (Visit 6 and 7) approximately 8 and 15 weeks, respectively, after the end of the Treatment Period for safety and PK assessments.

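### On the favoured reading of Protocol 8.4, a partner pregnancy that begins between Day 84 and Day 161 need not be notified; separately, no pregnancy test is scheduled on Day 1 before the first dose

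*Protocol*

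**What the plan says.** **Partner pregnancies.** Protocol 8.4 sets the condition for notification as follows: "If the female partner of a male participant becomes pregnant while the participant is receiving study drug or within the Safety Follow-up Period". What counts is when the partner becomes pregnant. Notification then follows the route for participants: a report within 24 hours of learning of the pregnancy, then the Exposure In Utero form. For a participant's own pregnancy, the same section uses a wider condition that covers the whole study as well as the Safety Follow-up Period. It also states: "A pregnancy is not considered to be an AE or SAE".

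**The periods.** Protocol 3.1.3 describes the Safety Follow-up Period through one visit: "Participants will return to the site for a Safety Follow-up Visit (Visit 5) approximately 4 weeks after the end of the Treatment Period". Protocol 3.1.4 describes a separate PK Period: "Participants will return to the site for 2 PK Visits (Visits 6 and 7) approximately 8 and 15 weeks, respectively" after treatment ends. Appendix A puts Visit 5 and Visits 6 and 7 under different column headings. SAP 2.2.1 counts "4 weeks for safety follow-up, and 11 weeks for PK assessments". No section states the day on which the Safety Follow-up Period ends.

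**Contraception.** Protocol 4.1 says: "Men whose partners are of childbearing potential must agree to use an effective method of avoiding pregnancy from screening to 90 days after". Here the count starts at the man's final visit.

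**Pregnancy testing.** Protocol 4.1 says: "Women of childbearing potential must have a negative urine pregnancy test at the Screening Visit". Section 8.7 and Appendix A schedule the urine test at Screening, Visit 7 and Early Termination only. Not being pregnant is part of inclusion criterion 2, and Appendix A footnote d has the site re-confirm the criteria on Day 1.

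**The concern.** The precaution and the reporting rule cover different spans of time. After about Day 84 the protocol still asks a male participant to prevent conception, still brings him to the site twice and still collects adverse events from him. On the favoured reading, however, a partner pregnancy that begins in that time creates no duty to notify and gives no clear trigger for follow-up to outcome.

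The other reporting routes do not fill the space. Section 8.4 says that a pregnancy is not an adverse event, and the definition in 8.1 concerns events in participants, which a partner is not. The rule in 8.3 for late SAEs judged related to study drug could at most reach an adverse outcome, not the pregnancy itself.

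The Day 1 point is smaller. Section 8.4 stops dosing immediately when a participant is found to be pregnant, but no test is scheduled immediately before the first dose. A pregnancy too early to show at Screening would not be tested for before dosing.

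**Working it through.** **Inputs**
- Last planned dose: Day 56 (Protocol 3.1.2).
- Visit 5: Day 84 ± 2. Visit 6: Day 112 ± 2. Visit 7: Day 161 ± 2 (Appendix A).
- Screening: Day -14 to Day -1 (Appendix A). There is no Day 0 (SAP 3.1.1).
- Contraception: to 90 days after the last visit (Protocol 4.1).

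**Reproducing the plan's own timeline**
- 56 + 4 × 7 = Day 84; 56 + 8 × 7 = Day 112; 56 + 15 × 7 = Day 161. These match Appendix A.
- SAP 2.2.1 total: 2 + 8 + 4 + 11 = 25 weeks, as stated.
- SAP PK time: 11 × 7 = 77 days. Day 161 − Day 84 = 77 days. The two agree, so the SAP's count places the end of safety follow-up at Day 84.

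**Partner gap for a completer, if the period ends at Visit 5**
- Nominal: 161 − 84 = 77 days.
- Shortest with windows: 159 − 86 = 73 days. Longest: 163 − 82 = 81 days.
- Time since the last planned dose: 84 − 56 = 28 days to 161 − 56 = 105 days.

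**Contraception rule for a completer**
- End: 161 + 90 = Day 251. This is 251 − 84 = 167 days beyond Day 84, made up of 77 days with visits and 90 days without.

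**Sensitivity to the reading**
- If the Safety Follow-up Period is read as running to Visit 7, the 77 days become 0. Only the 90 days after the last visit remain, and no visit is held in them.
- A man who stops early and whose last visit is the Safety Follow-up Visit, 4 weeks after his last dose (Protocol 4.5), does not have the 77-day gap.

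**What is and is not notifiable for a completer on the Day 84 reading**

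| Pregnancy | Learned of at | Duty under 8.4 |
|---|---|---|
| Partner, begins on treatment or by Day 84 | any visit, including 6 or 7 | yes |
| Partner, begins Day 84 to 161 | Visit 6 or 7 | none |
| Participant, begins any time to Visit 7 | any visit | yes |

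**Age of the pregnancy test at the first dose**
- Screening on Day -1: 1 day. Screening on Day -14: 14 days.
- Tests scheduled on Day 1: none.

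**The case against.** **The end date is a reading.** Section 3.1.3 names no last day, and Visits 6 and 7 have safety as well as PK purposes: adverse events are collected to Visit 7, and chemistry and hematology continue. A site could take safety follow-up to last until then. This stands in part. Day 84 is favoured by the separate sections, the Appendix A headings and the SAP's count, but it is not stated. If sites can read the period either way, the partner sentence needs an explicit date in any case.

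**The reporting window need not equal the contraception period.** One is a precaution for the participant and the other a duty of the site, and no text says they must coincide. This stands. Whether notification matters 28 to 105 days after a man's last dose depends on reproductive-toxicity and elimination data that neither document gives. A reader might infer exposure at conception from the objective "To assess the mean plasma levels of obicetrapib at steady state on Days 56, 84, 112, and 161", since Days 112 and 161 lie inside the gap. That shows only a plan to measure the drug then.

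**The Day 1 test is not required by the protocol's own rules.** The criterion asks for a negative test at Screening, and 8.7 and Appendix A agree with it. Footnote d asks for confirmation and updates, not repeat tests. Contraception is required from screening. All of this stands, so a reader who infers that the protocol contradicts itself on Day 1 goes too far. The documents do not require testing on Day 28 or Day 56 either.

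**Most pregnancies of interest are already covered.** This also stands. A reader might infer that any partner pregnancy reported at Visit 6 or 7 escapes notification. It does not, because the duty depends on when the pregnancy began and not on when the site hears of it. Nor is there a gap for participants during the study, since their condition is wider.

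**Conclusion.** The point holds in a limited form. For a completer, and on the reading that the Safety Follow-up Period ends at about Day 84, a partner pregnancy that begins in the following 77 days (73 to 81) carries no duty to notify. Section 8.4 does not forbid a report; it simply requires none. What the text establishes without any reading is that the partner condition is narrower than the participant condition and rests on a period with no stated end.

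The Day 1 test is a separate and inexpensive improvement.

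Required contraception should keep both kinds of event few. The documents give neither the number of women of childbearing potential nor the number of men with such partners, so no expected count can be given. The sample size and the primary LDL-C analysis are not affected.

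**What to change.** (a) In the partner sentence of Protocol 8.4, replace the reference to the Safety Follow-up Period with an explicit end date of at least Visit 7, in line with the participant sentence. Extending it to the end of the 4.1 contraception period (Day 251 for a completer) is optional. After Day 161 that would rely on the participant contacting the site.

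(b) In Protocol 8.7 and Appendix A, add the existing urine pregnancy test on Day 1, before the first dose, for women of childbearing potential.

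The cost is a few words in three places, a somewhat longer reporting duty for sites, and one urine test per woman of childbearing potential at a visit already held.
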